4.8.1.2 Deaths

The following deaths summaries will be generated on the all-treated population.

- Number (%) of patients who died during the study and reasons for death
- Number (%) of patients who died within 30 days after the last dose of study drug (excluding those who died after taking any subsequent anticancer therapy/procedure) and reasons for death

4.8.1.3 AE for Transplant patients

The following analysis will be performed for patients who have responded to loncastuximab tesirine and undergo SCT (either autologous or allogeneic) after permanent discontinuation of loncastuximab tesirine treatment without any intervening anticancer therapy. The data will include the following information reported until 180 days post-transplant regardless of relationship to loncastuximab tesirine.

- Summary of AEs \geq Grade 3 suggestive of hepatic toxicity, veno-occlusive disease/sinusoidal obstruction syndrome, graft-versus-host disease, infectious complications, prolonged cytopenia(s), and pulmonary toxicity
- Serious TEAEs by primary SOC, PT and Maximal CTCAE grade
- Number (%) of patients who died after transplant and reasons for death

Similar analysis will be performed for patients who receive CAR-T therapy after permanent discontinuation of loncastuximab tesirine treatment. The data will include the following information reported until 90 days after receiving CAR-T therapy regardless of relationship to loncastuximab tesirine.

- Summary of AEs \geq Grade 3 of cytokine release syndrome, encephalopathy, edema or effusion, rash, hepatic toxicity
- Serious TEAEs by primary SOC, PT and Maximal CTCAE grade
- Number (%) of patients who died after CAR-T therapy and reasons for death

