In late 2017, the US Food and Drug Administration (FDA) granted approval to the autologous anti-CD19 chimeric antigen receptor (CAR) T-cell therapy, axicabtagene ciloleucel (Yescarta[®]), for the treatment of adult patients with relapsed or refractory large B-cell lymphoma after two or more lines of systemic therapy, including DLBCL not otherwise specified, primary mediastinal large B-cell lymphoma, high-grade B-cell lymphoma, and DLBCL arising from follicular lymphoma. While this therapy does provide disease control in a portion of patients (51% CR, 21% partial response [PR]), and provides durable responses in patients who achieve a CR, the duration of response (DOR) is short for patients who only achieve a PR (2.1 months), meaning that a significant fraction of patients (approximately 50%) treated with this therapy will not have long-term disease control. In addition, this therapy has significant toxicity, with 94% of patients having cytokine release syndrome (13% Grade 3 or higher) and 57% having encephalopathy (29% Grade 3 or higher). It is only available at specialized centers and requires substantial lead-time for preparation, with approximately 10% of patients being unable to receive the planned therapy. Thus, the development of more effective salvage treatment remains an unmet medical need.

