4.7.3 Subsequent Anticancer Therapy or Procedure

Patients' subsequent anticancer therapies or procedures including systemic therapy, radiation, transplant, or other, along with the start date of new anticancer therapy or procedure will be collected and listed only.

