4.8.1 Adverse Events, Serious Adverse Events, and Deaths

4.8.1.1 Analyses of adverse events

The primary focus of adverse event reporting will be on TEAEs. An adverse event (AE) will be considered to be a TEAE if it begins or worsens on or after the first dose date and until 30 days after the last dose date, or start of a new anticancer therapy/procedure, whichever comes earlier.

An AE occurring before the first dose or more than 30 days after the last dose date or after the start of a new anticancer therapy/procedure will not be included in TEAE displays, but will be listed as non-TEAEs.

If an AE date/time of onset (occurrence, worsening, or becoming serious) is incomplete, an imputation algorithm will be used to classify the AE as pre-treatment, TEAE, or post-treatment. The algorithm for imputing date/time of onset will be conservative and will classify an AE as treatment-emergent unless there is definitive information to determine it is a non-TEAE (pre- or post-treatment). Some details on classification of AEs with missing or partial onset dates are provided in Section 7.

Analysis of all TEAE(s):

The following TEAE summaries will be generated for the all-treatment population.

- Overview of TEAEs, summarizing number of TEAE and number (%) of patients with any
 - TEAE
 - Related TEAE (including possibly related, probably related, or related)

- Any TEAE \geq Grade 3
- Serious TEAE
- TEAE leading to death
- TEAE leading to permanent treatment withdrawal
- TEAE leading to loncastuximab tesirine delay or reduction or interruption (if applicable)
- TEAE with at least one infusion related reaction
- All TEAEs \geq Grade 3 by PT, showing number (%) of patients with at least one TEAE, sorted by decreasing incidence of PTs
- All TEAEs by primary System Organ Class (SOC) and PT, showing number (%) of patients with at least one TEAE, sorted by SOC in alphabetic agreed order and decreasing incidence of PTs within SOC. This sorting order will be applied to all other tables, unless otherwise specified.
- All TEAEs by primary SOC, PT and Maximal CTCAE grade, showing number (%) of patients with at least one TEAE, sorted by SOC and PT in alphabetic order. This sorting order will be applied to all other tables, unless otherwise specified.
- All TEAEs \geq Grade 3 by primary SOC, PT and Maximal CTCAE grade
- All related TEAEs by primary SOC, PT and Maximal CTCAE grade (including possibly related, probably related, or related)

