- All TEAEs leading to treatment withdrawal by primary SOC, PT and Maximal CTCAE grade
- All TEAEs leading to dose delay by primary SOC, PT and Maximal CTCAE grade
- All TEAEs leading to dose reduction by primary SOC, PT and Maximal CTCAE grade
- All TEAEs leading to infusion interruption by primary SOC, PT and Maximal CTCAE grade
- All TEAEs with fatal outcome by primary SOC, PT and Maximal CTCAE grade
- All Serious TEAEs by primary SOC, PT and Maximal CTCAE grade
- All infusion related reaction TEAEs by primary SOC, PT and Maximal CTCAE grade
- Summary of grouped TEAEs selected by Standardised MedDRA Query (SMQ), ADCT modified SMQ will also be provided by primary Grouped terms, PT and Maximal CTCAE grade. These group term include: effusion/edema, hepatic, fatigue, skin/nail, pain.

- Summary of TEAEs will also be provided by demographic factors including: sex, age group, race, disease subtype if appropriate.

All TEAEs, all serious adverse events (SAEs), all TEAEs leading to treatment withdrawal, all TEAEs leading to dose reduction, all TEAEs leading to dose delay, all TEAEs considered infusion related reactions, all TEAEs with fatal outcome and non-TEAEs will be listed.

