4.9.2 Duration of Response

Duration of response will be defined for patients with CR or PR only as the interval between the date of initial documentation of a response and the date of the first documented evidence of progressive disease based on independent radiographic assessment or death, whichever occurs first. Clinical progression at EOT/EOS without radiographic assessment could be considered as an event in a sensitivity analysis. Patients who have the event after the start of subsequent anticancer therapy/procedure, or are progression-free and alive at the time of clinical cut-off, or have unknown status, will be censored at the last valid tumor assessment on or before the start of subsequent anticancer therapy/procedure or clinical cut-off time. When a subsequent anticancer therapy is used and progressive disease (based on radiographic or clinical progression at EOT/EOS) is observed within 6 days, they will be considered as the same visit (within the protocol specified +/-6 days visit window) and the patient will be counted as having an event (losing the response).

Patients with no post-baseline disease assessment will be censored on Day 1.

Duration of response will be estimated and displayed for the all-treated population using Kaplan-Meier methods (SAS[®] PROC LIFETEST). A Kaplan-Meier plot will be presented.

A sensitivity analysis of DOR will be conducted in which the DOR for patients undergo SCT will not be censored at SCT.

A sensitivity analysis of DOR per investigator assessments will also be conducted.

Subgroup analysis may be provided for disease subtype, disease stage, double/triple hit (yes/no), bulky disease (yes/no), GCB/ABC, transformed (yes/no), age group, response to the first line and/or most recent line of prior systematic therapy (relapse: CR+PR vs. refractory: SD+PD vs. other: NE + missing), best response to loncastuximab tesirine (CR/PR), and other relevant variables.

4.9.3 Time to Response:

Time to response (TTR) is defined among patients who achieve either CR or PR as BOR before the start of subsequent anticancer therapy or procedure as the time from the first dose to the initial documented response. For this subset of patients, TTR will be summarized using descriptive statistics.

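### SAP 4.8.1.3 limits the post-SCT and post-CAR-T serious-event tables to TEAEs, a term that by definition excludes almost everything those tables are meant to show

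*SAP*

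**What the plan says.** SAP 4.8.1.3 describes two groups: responders who undergo SCT after stopping study drug with no other therapy in between, and patients who receive CAR-T after stopping study drug. For each group a lead-in sets the data window (up to 180 days after transplant, or 90 days after CAR-T, whatever the judged causality). Three summaries follow: selected Grade ≥3 AEs, serious events and deaths. In both lists the serious-event item is "Serious TEAEs by primary SOC, PT and Maximal CTCAE grade".

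TEAE is a defined term. Under SAP 4.8.1.1 an event qualifies if it begins or worsens from first dose "until 30 days after the last dose date, or start of a new anticancer therapy/procedure, whichever comes earlier". The same section adds that an AE occurring "after the start of a new anticancer therapy/procedure will not be included in TEAE displays"; such events are listed as non-TEAEs.

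Protocol 8.2.2 ends routine AE/SAE reporting at 30 days after last dose or the start of new therapy, after which only related SAEs are reported. It then makes two exceptions, for SCT and CAR-T patients, under which SAEs are reported over the same 180- and 90-day windows regardless of causality. Appendix 2 tables 14.3.3.4.26 (SCT) and 14.3.3.4.28 (CAR-T) are titled as serious adverse events, without the treatment-emergent qualifier.

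**The concern.** The lead-ins promise post-procedure data, but the bullet applies a filter that stops at the procedure. A programmer who applies the defined term would produce tables that are empty or show mainly events that began before the transplant or CAR-T infusion. The extra SAEs that the protocol extends reporting to capture would not be tabulated.

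No other planned table covers this. The Grade ≥3 summaries in 4.8.1.3 are confined to named conditions, so the two serious-event tables are the only ones planned to show all types of SAE after SCT or CAR-T by system organ class, preferred term and grade.

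**Working it through.** This is a question of definitions, so the check sets the sections side by side and then compares the two windows. The plan gives no figure of its own to reproduce.

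**1. Do SCT and CAR-T close the TEAE window?**
- SCT: yes. SAP 4.7.3 speaks of "subsequent anticancer therapies or procedures including systemic therapy, radiation, transplant, or other". SAP 4.9.2 also treats SCT as a censoring event by default: "A sensitivity analysis of DOR will be conducted in which the DOR for patients undergo SCT will not be censored at SCT".
- CAR-T: SAP 4.7.3 does not name it, but it fits the systemic-therapy or other category. Protocol 1.1 describes a CAR-T product as approved "for the treatment of adult patients with relapsed or refractory large B-cell lymphoma after two or more lines of systemic therapy".

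**2. Which summaries carry the TEAE limit?**

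| Summary in SAP 4.8.1.3 | After SCT | After CAR-T |
|---|---|---|
| Selected Grade ≥3 AEs | no TEAE limit | no TEAE limit |
| Serious events | **TEAEs only** | **TEAEs only** |
| Deaths | no TEAE limit | no TEAE limit |

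That is 2 of 6.

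**3. Window overlap.** Let L be the last dose and T the day of the procedure (day 0).

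TEAE window end = min(L + 30 days, start of new therapy or procedure) ≤ T.

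- SCT, days 0 to 180 = 181 calendar days. At most day 0 lies inside: 1/181 = 0.55%. Days 1 to 180: 0 of 180.
- CAR-T, days 0 to 90 = 91 calendar days. At most day 0 lies inside: 1/91 = 1.10%. Days 1 to 90: 0 of 90.

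Day 0 is left open because 4.8.1.1 includes events until the start of the new therapy and excludes events after it, without placing an event on the day itself.

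**4. Incomplete onset dates.** These are a second possible exception and are not counted above. For them the SAP's algorithm "will classify an AE as treatment-emergent unless there is definitive information to determine it is a non-TEAE", so some post-procedure events with partial dates could enter a TEAE table.

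**5. Does the result depend on step 1?** Suppose the procedure did not close the window and only the 30-day limit applied. Both groups have stopped study drug, so take T ≥ L + 1. The post-procedure days covered are then at most (L + 30) − (L + 1) = 29.
- SCT: at least 180 − 29 = 151 of 180 days still fall outside.
- CAR-T: at least 90 − 29 = 61 of 90 days still fall outside.

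Most of each window is lost either way.

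**6. Likely origin.** The main safety section, 4.8.1.1, has the bullet "All Serious TEAEs by primary SOC, PT and Maximal CTCAE grade". The two bullets in 4.8.1.3 match it apart from the first word, which points to a drafting carry-over.

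**The case against.** The strongest reply is that the SAP already shows what is meant. Appendix 2 describes itself as programming instruction, and its titles for these two tables omit the treatment-emergent qualifier, although the appendix uses that qualifier elsewhere (for example table 14.3.3.4.2). The lead-ins set a specific window, and a specific rule would normally prevail over a general definition. On that reading a wrong table is possible but unlikely. This stands as evidence of intent. It does not settle the matter: the appendix also says its list may change without a SAP update, and nothing in the SAP says that a lead-in or a table title overrides a defined term in the body.

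A second reply is that protocol 8.2.2 governs what is reported, not what is tabulated, and that protocol 9.7.1 centres AE summaries on TEAEs. That is a fair refinement. A TEAE-only table breaks no collection rule; it fails to display the data the rule was written to obtain.

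Third, nothing is lost. All SAEs are listed (SAP 4.8.1.1; listing 16.4.2.2 for the non-treatment-emergent ones), and deaths and selected Grade ≥3 events are tabulated without the limit. This is correct and keeps the point minor, but a listing gives no incidence by organ class, term and grade.

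Fourth, the lead-ins state when the window ends but not when it starts, so simply dropping the TEAE limit could mix earlier SAEs with post-procedure ones. The gap is real. It already exists in the current text and applies equally to the Grade ≥3 bullets, so it is a separate matter and no reason to keep the TEAE limit.

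**Conclusion.** The point holds. As written, the two serious-event bullets exclude serious events that start after SCT or CAR-T, apart from possible procedure-day events and events with incomplete onset dates. They are inconsistent with the section's own lead-ins and with the Appendix 2 titles, and they undo the purpose of the reporting exceptions in protocol 8.2.2.

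The day counts describe the window only. The documents give no number of SCT or CAR-T patients or of their events, so the number of events that would be missed cannot be estimated. The conclusion counts CAR-T as a new anticancer therapy, but the 30-day limit alone would still remove most of its window. The defect is confined to descriptive safety tables; the primary endpoint and type I error are unaffected. It should be corrected, because the rule as stated gives the wrong table and the correction is easy.

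**What to change.** In both serious-event bullets of SAP 4.8.1.3, replace *Serious TEAEs* with *SAEs (not limited to TEAEs)*. Keep the lead-ins as they are and add no new restriction on the start of the window. The Grade ≥3 and death bullets need no change. The body text then agrees with protocol 8.2.2 and with tables 14.3.3.4.26 and 14.3.3.4.28, and no event within the 180- or 90-day window is dropped for being non-treatment-emergent.

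The cost is a wording change in two bullets, with no new data, table or analysis.

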4.8.2 Laboratory Data

Laboratory data of hematology, biochemistry, and coagulation up to 30 days after the last dose of study drug or the end of treatment visit date, whichever is later, will be reported in SI units. Descriptive statistics (mean, standard deviation, median, and range) will be calculated for the raw data and for their changes from baseline at each scheduled assessment.

All results will be summarized using shift from baseline. Shifts for clinical laboratory results that can be graded according to CTCAE version 4.0 will be summarized by CTCAE grade.

Summaries by visit will include data from scheduled assessments, and all data will be reported according to the nominal visit date for which it was recorded. Unscheduled data will be included in “worst case post-baseline” summaries, which will capture a worst case across all scheduled and unscheduled visits after the first dose of study treatment.

Summary analyses will include data up to the start of subsequent anticancer therapy/procedure.

All laboratory data, including urinalysis, will be listed. Pregnancy test results will not be listed, but will be included in datasets.

4.8.3 Electrocardiogram

Descriptive statistics (mean, standard deviation, median and range) for ECG data will be calculated for the raw data and for their changes from baseline at each scheduled assessment.

The following abnormal QTc (including QTcF and QTcB) will be reported by a frequency table:

At any post-baseline with absolute value

>450 - <=480 ms

>480 - <=500 ms

> 500 ms

Change from Baseline

>30 – <=60 ms

>60 ms

Summary analyses will include data up to the start of subsequent anticancer therapy/procedure.

All ECG data will be listed, both for quantitative data and for overall impression.

4.8.4 Vital Signs

Descriptive statistics (mean, standard deviation, median, and range) for vital signs data, including systolic and diastolic blood pressure, heart rate, respiration rate, and body temperature will be calculated for the raw data and for their changes from baseline at each scheduled assessment.

Summary analyses will include data up to the start of subsequent anticancer therapy/procedure.

All vital signs data will be listed together with body weight.

4.8.5 ECOG Performance Status

Descriptive statistics (mean, standard deviation, median and range) will be calculated for the raw data and for their changes from baseline at each scheduled assessment.

Summary analyses will include data up to the start of subsequent anticancer therapy/procedure.

ECOG performance score data will be listed.

4.8.6 Physical Examinations and Body Weight

Physical examination will be performed according to protocol. Clinically significant findings from the physical examinations will be recorded as medical history (prior to first administration of loncastuximab tesirine) or AEs (subsequent to first administration of loncastuximab tesirine).

Body weight will be listed together with vital signs.

4.9 Efficacy Analyses

Disease assessment will be performed according to protocol. The endpoints described in this section, if not mentioned specifically, use the independent reviewer's evaluation according to the 2014 Lugano Classification criteria before the start of subsequent anticancer therapy or procedure.

Lesion assessment data (target lesions, non-target lesions, and new lesions) and tumor response will be listed. A separate listing will contain derived data for duration of response (DOR), relapse-free survival (RFS), progression-free survival (PFS), and Overall survival (OS).

4.9.1 Overall Response Rate

Overall response rate is defined as the proportion of patients who achieve either CR or PR as best overall response (BOR) as determined by central review according to the 2014 Lugano Classification criteria before the start of subsequent anticancer therapy or procedure. For the primary ORR analysis in the all-treated population, patients with a CR or PR will be counted as successes and all other patients (including those with missing response information) will be counted as failures.

The order of overall response category is: CR, PR, SD, NE, PD (including disease recurrence/ relapse). The overall response category will be derived based on response assessment performed on or before the start of subsequent anticancer therapy/procedure. Patients without documented subsequent anticancer therapy and/or with missing start date of anticancer therapy will be considered as not having received subsequent anticancer therapy. A BOR of SD can only be made after the patient is on-study for a minimum of 35 days after the first dose of study drug. Any tumor assessment indicating SD before this time period will be considered as NE for BOR if no assessment after this time period is available.

The overall response rate and the corresponding 95% two-sided exact confidence interval will be presented. Subgroup analysis may be provided for disease subtype, disease stage, double/triple hit (yes/no), bulky disease (yes/no), GCB/ABC, transformed (yes/no), age group, sex, country, response to the first line and/or most recent line of prior systematic therapy (relapse: CR+PR vs. refractory: SD+PD vs. other: NE + missing), and other relevant variables.

Percent change from baseline in the sum of product of the perpendicular diameters (SPD) for target lesions will be presented for available data in the all-treated population. These data will also be displayed as a waterfall plot, with vertical bars representing the sorted values of best percent reduction for each patient.

A sensitivity analysis of ORR determined by the independent reviewer's evaluation will be conducted for the per-protocol population if relevant.

A sensitivity analysis of ORR will be conducted in which best overall response is determined by investigators.

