8.1 Efficacy Assessments

Disease assessments will occur as per schedule of events (SoE) ([Table 1](#)) until progression. Disease assessments should take place at the timepoints specified even if study drug dosing is delayed. Additional disease assessments may be obtained, if clinically indicated.

Imaging and clinical examination for lymphoma will be performed at all disease assessment timepoints. All patients will have positron emission tomography - computed tomography (PET-CT) of the neck/chest/abdomen/pelvis and other areas of known or suspected disease performed at baseline. Patients with PET-avid disease at baseline should have PET-CT for all subsequent disease assessments. If disease is not PET-avid at baseline, computed tomography (CT) or magnetic resonance imaging (MRI) may be used for subsequent disease assessments. Patients whose disease is not PET-avid should have a bone marrow biopsy as part of their baseline staging and disease assessment if clinically appropriate.

Screening (Baseline) imaging must be performed within 4 weeks prior to C1D1.

During the treatment period, imaging will be performed 6 weeks and 12 weeks after C1D1, then every 9 weeks until EOT. Week 6 imaging should be performed within 5 days prior to C3D1 and Week 12 imaging should be performed within 5 days prior to C5D1. All other imaging should be performed within ± 2 weeks of the scheduled time point.

During the follow-up period, patients who discontinued study drug for reasons other than disease progression or initiation of other anti-cancer therapy except stem cell transplant, will have imaging performed every 12 (± 2) weeks until 1 year from EOT, then every 6 months until disease progression, up to 3 years from EOT.

Response data will be collected for patients who receive CAR-T therapy until 90 days after receiving CAR-T therapy.

If a scan has been performed within 8 weeks of EOT, it does not need to be repeated at EOT.

In case of dose delays, disease assessment should be maintained at the frequencies defined above.

The patient's response to treatment will be determined according to the 2014 Lugano Classification Criteria ([Appendix 2](#)) as CR, PR, stable disease (SD), or progressive disease (PD). Images will be obtained according to local site imaging protocols and will be submitted for central review. Submission instructions for central review will be provided in a separate manual.

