8.2.2 Eliciting and Reporting Adverse Events/Serious Adverse Events

Patients will be instructed to contact the Investigator at any time after ICF signature if any symptoms develop. At each study visit, patients will be asked a non-leading question to elicit any medically related changes in their well-being. Patients may also report AEs voluntarily and they will be instructed to contact the Investigator between visits if any symptoms develop or worsen.

AEs will be reported starting when the patient provides written informed consent. Clinically significant medical conditions present at the time of ICF signature will be reported as medical history. Clinically significant medical conditions that start or worsen after ICF signature will be reported as AEs.

All AE/SAEs, regardless of relationship to study drug, will be reported from the time the patient signs the ICF until 30 days after the last dose of study drug or start of new anti-cancer therapy, whichever is earlier; thereafter, only related SAEs will be reported, with 2 exceptions.

1. Patients who have responded to loncastuximab tesirine and undergo SCT (either autologous or allogeneic) after permanent discontinuation of loncastuximab tesirine treatment without any intervening anti-cancer therapy. These patients will have the following safety information reported until 180 days post-transplant regardless of relationship to loncastuximab tesirine:
 - Grade ≥ 3 AEs suggestive of hepatic toxicity, veno-occlusive disease/sinusoidal obstruction syndrome, graft-versus-host disease, infectious complications, prolonged cytopenia(s), and pulmonary toxicity
 - SAEs
 - Death

2. Patients who receive CAR-T therapy after permanent discontinuation of loncastuximab tesirine treatment will have the following safety information reported until 90 days after receiving CAR-T therapy regardless of relationship to loncastuximab tesirine:
 - Grade ≥ 3 AEs of cytokine release syndrome, encephalopathy, edema or effusion, rash, hepatic toxicity
 - SAEs
 - Death

Whenever possible, AEs should be reported as a diagnosis rather than individual signs and symptoms. If no diagnosis is available or has been identified, then the primary symptom is reported.

In general, the term ‘disease progression’ should not be used for reporting an AE/SAE. However, AEs/SAEs that are complications of disease progression should be reported.

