9.6.1 Overall Response Rate

The ORR will be defined as the proportion of patients with a BOR of CR or PR. The overall response category will be derived based on response assessment performed on or before the start of subsequent anti-cancer therapy. For the primary ORR analysis in the all treated population, patients with a CR or PR will be counted as successes and all other patients (including those with missing response information) will be counted as failures.

The percentage of ORR with its 95% confidence interval (CI) will be presented. In contrast to CR, PR, or PD, a BOR of SD can only be made after the patient is on-study for a minimum of 35 days after the first dose of study drug. Any tumor assessment indicating SD before this time period will be considered as a non-evaluable for BOR if no assessment after this time period is available.

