7.1 General conventions

7.1.1 Missing data

Handling of missing/partial dates

In general, imputation of missing dates will be made for AE onset date, AE resolution date, date of death, medication start/end dates, start and end dates of prior and subsequent therapies, and date of initial diagnosis for reporting. No imputation should be done at the data level.

- If dates are completely missing, no imputation will be made.
- For any partial date with missing year, no imputation will be made.
- For missing initial diagnosis date and subsequent therapies, if only day is missing, then the 15th of the month will be used; if only year is present, then June 30th will be used. If such imputed date for initial diagnosis is on or after date of first dose, then date of first dose - 1 will be used. If such imputed date for subsequent therapies is before date of last dose, then date of last dose +1 will be used.
- If the imputed date is for an AE start date and is in the same year and month as but before the first dose date, then the first dose date will be used, or if the imputed AE start date is after the AE end date, then the AE end date will be used. If the imputed date is for an AE start date and is in the same year and month as but after the last dose date + 30 days, then the last dose date + 30 days will be used.
- If a medication date or time is missing or partially missing, so it cannot be determined whether it was taken prior or concomitantly, it will be considered as a prior and concomitant medication.
- If the imputed date is for a date of death and is before the last date that the patient is known to be alive, the latter date will be used.
- If the date part is missing for new anticancer therapy, the month and year will be used for comparison with disease assessment.

Handling of missing relationship to investigational product of TEAEs

If the assessment of the relationship to IP is missing, then the relationship to IP has to be assumed and the TEAE considered as such in the frequency tables of possibly related TEAEs, but no imputation should be done at the data level.

Handling of missing severity/grades of AEs

If the severity/grade is missing for one of the treatment emergent occurrences of an AE, the maximal severity of the remaining occurrences will be considered. If the severity is missing for all the occurrences a “missing” category will be added in summary table.

No other imputation of values for missing data will be performed.

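### SAP 4.9.1 treats documented but undated subsequent therapy as never given, which removes the response cut-off for those patients and can only raise ORR and CR rate (minor)

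*SAP*

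**What the plan says.** Protocol 9.6.1 sets the cut-off: "The overall response category will be derived based on response assessment performed on or before the start of subsequent anti-cancer therapy". It makes no exception. SAP 4.9.1 defines ORR with the same cut-off, and SAP 3.3 declares no modification to the protocol's statistical section.

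The same paragraph of SAP 4.9.1 then deals with two groups in one sentence: patients with no documented subsequent therapy, and those "with missing start date of anticancer therapy will be considered as not having received subsequent anticancer therapy". The first group is uncontroversial. The second includes patients known to have had later therapy.

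SAP 7.1.1 covers missing dates:
- Completely missing: "If dates are completely missing, no imputation will be made". A partial date without a year is not imputed either.
- Partial dates with a year: imputation is introduced for "start and end dates of prior and subsequent therapies, and date of initial diagnosis for reporting". A separate bullet covers efficacy: "If the date part is missing for new anticancer therapy, the month and year will be used for comparison with disease assessment".

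Protocol 8.1 continues follow-up imaging for "patients who discontinued study drug for reasons other than disease progression or initiation of other anti-cancer therapy except stem cell transplant". Imaging therefore goes on after a transplant, and that exception is not limited to responders. Protocol 8.1 also collects response data for 90 days after CAR-T therapy, and SAP 4.9.8 summarises those data separately.

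**The concern.** A patient with recorded later therapy and an empty start-date field is analysed as though the therapy never happened. Every later scan then enters best overall response, including scans that reflect the later therapy. This conflicts with Protocol 9.6.1 and with the SAP's own definition of ORR.

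The direction is fixed. SAP 4.9.1 ranks response as CR, PR, SD, NE, PD and takes the best, so an additional scan can keep or raise the category but never lower it. Missing data on the primary endpoint here favour the drug, whereas the same section counts missing response as failure.

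No planned analysis varies the rule. The two ORR sensitivity analyses change the population (per-protocol) or the assessor (investigator). DOR, RFS and PFS each have an analysis that does not censor at transplant, but ORR has no transplant analysis. SAP 4.9.2, 4.9.5 and 4.9.6 do not say whether the missing-date rule also removes censoring at subsequent therapy. For those endpoints the direction would not be fixed, because lost censoring can add events as well as follow-up time.

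**Working it through.** **Inputs.** N = 140, null ORR 20%, alternative 40%, one-sided alpha 0.025, exact binomial test (Protocol 9.1 and 9.4; SAP 3.1 and 6). Phase 1 DLBCL CR rate 22/92 (Protocol 1.3). The number of patients with undated therapy and a later CR or PR is not given. One such patient is taken for illustration, with 0 to 3 as an assumed range.

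**The plan's own figure.** With X ~ Binomial(140, 0.20), P(X ≥ 38) = 0.0254 and P(X ≥ 39) = 0.0158, so the critical count is 39. At 40%, P(X ≥ 39) = 0.9990. The stated power of more than 99% is reproduced, and this issue does not touch it.

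**Which dates lose the cut-off.**
- Completely missing, or no year: nothing is imputed and SAP 4.9.1 calls the patient untreated. The cut-off is lost.
- Day missing: month and year are compared with the scan, and the on-or-before wording settles a same-month tie. A cut-off remains.
- Year only: the reporting rule says "if only year is present, then June 30th will be used", but the efficacy bullet needs a month. This case is arguable.

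**Which patients could be affected.** Scheduled imaging stops at new therapy other than transplant. What remains is mainly a patient with stable disease who has an undated transplant and then a centrally read CR or PR. CAR-T is a possible second route, because SAP 4.9.8 does not expressly exclude those responses from ORR.

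**Effect on the estimates, per patient.** 1/140 = 0.71 percentage points. Intervals are exact (Clopper-Pearson) 95%.
- ORR at the planned 40%: 56/140 = 40.0% (31.8 to 48.6) becomes 57/140 = 40.7% (32.5 to 49.3).
- CR rate at the Phase 1 level (22/92 × 140 = 33.5, taken as 33): 33/140 = 23.6% (16.8 to 31.5) becomes 34/140 = 24.3% (17.4 to 32.2).

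**Effect on the test.** An affected patient is a true non-responder, so the other 139 decide. One false responder changes the result only if exactly 38 of those 139 respond:

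| True ORR | P(X = 38), X ~ Binomial(139, ORR) |
|---|---|
| 40% | 0.0006 (0.06%) |
| 35% | 0.0117 (1.2%) |
| 30% | 0.0597 (6.0%) |

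**Type I error.** If k non-responders were always counted as responders, the error at a true ORR of 20% is P(X ≥ 39 − k) with X ~ Binomial(140 − k, 0.20). This gives 0.0158, 0.0228, 0.0323 and 0.0452 for k = 0, 1, 2 and 3. The nominal 0.025 is exceeded only from k = 2.

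**The case against.** The strongest reply is that the case is close to hypothetical. Start dates are to be collected (SAP 4.7.3). The Schedule of Events records the first new anticancer treatment during 12-weekly follow-up, so a therapy reported there is bracketed to about 12 weeks and a date missing even its year should be resolved by query. Subsequent therapies (listing 16.1.12), tumor evaluations (listing 16.2.1) and swimmer plots are planned, so an affected patient should be identifiable. All of this stands, and it is why the point is minor. It does not make the rule right: the rule is written for the residue that queries fail to resolve, and no count of that residue is planned.

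Three stronger readings are tempting, and the documents do not support them.
- A reader might infer that partly missing dates also lose the cut-off, or that SAP 7.1.1 contradicts itself. It does not: the 15th and June 30th imputations are introduced for reporting, and a separate bullet governs comparison with scans. Only year-only dates are left open.
- A reader might infer that a PR could readily become a CR after an undated transplant. That route is largely closed. Protocol 8.2.2 follows "Patients who have responded to loncastuximab tesirine and undergo SCT" without intervening therapy to 180 days after transplant, and SAP 4.8.1.3 analyses that window, so the transplant date is needed. With other intervening therapy, scheduled imaging stops.
- A reader might infer that CAR-T responses will be counted in ORR. The separate summary is probably meant to keep them out. The text just does not say so.

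**Conclusion.** The point holds and is minor. SAP 4.9.1 states a rule that contradicts Protocol 9.6.1 and its own definition of ORR for documented therapy with no usable start date, and any error raises ORR and the CR rate. The size is 0.71 points per affected patient, in a number that the documents do not give and that is probably zero or very few.

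A reader might infer that the primary conclusion is at risk. Near the planned 40% it is not: 56 expected responders lie 17 above the critical count of 39, and one affected patient would decide the result with probability 0.06%. That chance reaches 6.0% only if the true ORR is 30% and such a patient exists. Sample size, critical count and power are unchanged.

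The figures assume exactly 140 treated patients, independent responses, and an affected patient who is a true non-responder on study drug.

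**What to change.** In SAP 4.9.1:
- Delete the missing-start-date limb, so that the sentence covers only patients with no documented subsequent therapy.
- State that, for documented therapy with no usable start date after query, only assessments on or before the EOT visit count for best overall response. If there was no EOT visit, only assessments on or before the last dose count.
- Report the number of such patients, and show ORR and CR rate under the current SAP rule as a sensitivity row.

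In SAP 4.9.2, 4.9.5 and 4.9.6, state whether the same cut-off sets censoring. SAP 7.1.1 needs no rewrite.

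The cost is a few lines of SAP text, one count and one table row. The price in the main figure is that a genuine response first seen after the cut-off may be lost, although Protocol 9.4 and SAP 6 expect some late responses; for example, a patient dosed once with no EOT visit would lose the Week 6 scan. The sensitivity row shows any such loss. The EOT cut-off is also an approximation, because Protocol 4.4 only prefers that the visit precede new therapy, so a late EOT scan could still follow it. If the count is zero, reporting that closes the question.
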